## **2.2 SCREENING EVALUATION**

Study eligibility is based on meeting all of the study inclusion criteria and none of the exclusion criteria at screening before study treatment administration. Screening evaluations may be performed as part of an NIH Screening protocol. This does not include the baseline correlative studies that will only be performed after the patient has signed the consent form for this protocol.

- 2.2.1 Within 14 days prior to subject enrollment, unless otherwise indicated below:
  - 2.2.1.1 Complete history and physical examination, including ECOG status, weight, vital signs, and oxygen saturation by pulse oximetry at rest and after exertion.
  - 2.2.1.2 Confirmation of the diagnosis of RRP by pathology report from a CLIA-certified laboratory (no time limit).
  - 2.2.1.3 Clinic-based flexible nasopharyngolaryngoscopy and/or tracheoscopy to document disease to the extent that can be evaluated without sedation or general anesthesia. This will include standard bright light endoscopy and may include videostroboscopy. Endoscopy may be omitted in patients with disease that is not endoscopically accessible. This examination will allow determination of a Derkay score that will determine if the patient meets inclusion criteria.
  - 2.2.1.4 Computed tomography scan of the neck and/or chest if patients have known or suspected pulmonary RRP. This examination could also be used to determine if the patient meets inclusion criteria.
  - 2.2.1.5 Hepatitis and HIV testing as detailed in sections **2.1.1.8 - 2.1.1.10** (within 90 days prior to subject enrollment).

2.2.2 Within 3 days prior to subject receiving the first dose of study drug:

2.2.2.1 CBC w/differential, chemistry panel including: LDH, AST, ALT, ALP, T.Bili, BUN or serum urea level, creatinine, Ca, Mg, Na, K, Cl, glucose, amylase, lipase, TSH, free T4, free T3

2.2.2.2 Pregnancy test in women of childbearing potential.

2.2.2.3 Review of concomitant medications

### **2.3 BASELINE EVALUATION**

After consenting to enrollment in this study, baseline evaluation will include exam under anesthesia (sedation or general anesthesia) including rigid and/or flexible endoscopy to thoroughly assess airway patency and the extent of disease, rule out invasive cancer, debulk lesions that pose a major risk of airway obstruction, and obtain papilloma and normal mucosa tissue for research. Baseline imaging studies will be done if imaging is used for response assessment. For other baseline evaluations please refer to the Study Calendar (Section 3.5).

### **2.4 PARTICIPANT REGISTRATION AND STATUS UPDATE PROCEDURES**

Registration and status updates (e.g., when a participant is taken off protocol therapy and when a participant is taken off-study) will take place per CCR SOP ADCR-2, CCR Participant Registration & Status Updates found [here](#).

applicable. If patients have a complete response or no response, treatment will be discontinued at that time. If patients have a partial response, treatment will be continued for up to 6 additional weeks (12 weeks total treatment) or until disease progression or complete response. If subjects demonstrate a partial response and receive an additional 6 weeks of treatment their responses will again be measured after completing this additional treatment (+/- 7 days). At the conclusion of treatment all patients will undergo EUA and endoscopy with either standard of care surgical debulking of their disease or biopsies to confirm complete regression of papillomatous disease. The primary endpoint of this study is complete response to treatment, but patients will be followed long-term after completion of treatment to assess timing and frequency of future interventions.

If a patient's condition precludes safe performance of any protocol-driven biopsy, apheresis or other research procedure, the procedure may be delayed for an additional two weeks or canceled at the discretion of the investigator. This will not be considered a protocol deviation. Endoscopy may be omitted in patients with disease that is not endoscopically accessible.

3.1.2 Protocol Schema

### **3.2 DRUG ADMINISTRATION**

#### **3.2.1 Avelumab**

Avelumab will be administered at a dose of 10 mg/kg IV every other week for up to 12 weeks total (6 cycles). All patients will be pre-treated with an antihistamine and acetaminophen 30-60 minutes prior to each dose (for example, 25-50 mg diphenhydramine and 500-650 mg acetaminophen). Avelumab is to be diluted in 250 mL of 0.45% or 0.9% saline solution (sodium chloride injection) and administered as an IV infusion, using a volumetric pump with a 0.2/0.22 micron in-line filter at the protocol-specified dose. It is not to be administered as an IV push or bolus injection.

Avelumab will be infused at 60 mL/hour for 10 minutes; if no infusion reaction observed then rate will be increased to 120 mL/hour for 10 minutes; if no infusion reaction observed then rate will be increased to 250 mL/hour for the remainder of the infusion. If infusion reactions are observed, the infusion rate may be decreased to the previous rate at which it was tolerated. At the end of the infusion, flush the line with a sufficient quantity of normal saline.

Avelumab will be infused in the NIH Clinical Center Day Hospital or on an inpatient oncology ward. Vital signs (blood pressure, pulse, respiration, temperature) will be assessed before infusion, at each rate change, at completion of infusion, and every 1 hour (+/- 15 minutes) or more frequently as clinically indicated for 2 hours after completion of the infusion or until stable.

Medications readily available for the emergency management of anaphylactoid reactions should include: epinephrine (1:1000, 1 mg/mL) for subcutaneous injection, diphenhydramine hydrochloride for intravenous injection, and resuscitation equipment.

##### **3.2.1.1 Overall summary of the treatment plan**

Drug	Dose	Days
Avelumab	10 mg/kg IV	Day 1 of a 14 day cycle (every other week) for up to 12 weeks total treatment (6 cycles)

Response will be assessed by flexible endoscopy with or without imaging studies before treatment and 6 and 12 weeks after starting treatment.

### **3.3 ON-STUDY ASSESSMENTS**

If doses are delayed, assessments and research studies will be postponed accordingly.

#### **3.3.1 Prior to each dose within 3 days of drug administration**

- Targeted physical examination if clinically indicated which may include clinic-based flexible nasopharyngolaryngoscopy and/or tracheoscopy with assignment of a Derkay score if the Derkay score is being used as the primary response assessment
- Vital signs and oxygen saturation at rest and after exertion
- Assess for symptoms of myocarditis (chest pain, shortness of breath, swelling of ankles or feet)
- Pregnancy test in women of childbearing potential

- CBC w/differential, LFTs (ALT, AST, total bilirubin, alkaline phosphatase), BUN or serum urea level, creatinine, Ca, Mg, Na, K, Cl, LDH, glucose, amylase, lipase, TSH with reflexive Free T4, Free T3
  - TBNK
  - Adverse events assessment
  - Research blood:
    - 6 Cell Preparation Tubes (CPT) (48 mL) will be collected for immunological testing and processed as described in section 4.1.1. Attention [name], [name] contact [contact].
    - 1 Serum Separator Tubes (SST) (8 mL) will be obtained for serum collection and processed as described in section 4.1.1 . Attention [name], [name] contact [contact].
  - Review of concomitant medications
  - Voice Handicap Index-10 assessment questionnaire
- 3.3.2 Additional studies at a single time point two weeks after the first dose of avelumab
- Leukapheresis (see Section 4.1.1)
  - Exam under anesthesia (sedation or general anesthesia) including rigid and/or flexible endoscopy with biopsies to assess disease response, clinical signs of inflammation or airway compromise, and to obtain biopsies for research.
- 3.3.3 Every 6 week (3 cycles) (+/- 7 days) response assessment (performed at 6 and 12 weeks after first dose of avelumab)
- Interval targeted history and physical.
  - Clinic-based flexible nasopharyngolaryngoscopy and/or tracheoscopy. This will include standard bright light endoscopy and videostroboscopy, and assignment of a Derkay score. This endoscopic examination combined with radiographic examination (if radiographically measurable disease is present) will be used to determine response to treatment.
  - Voice Handicap Index-10 assessment questionnaire, see Section 12.2.
  - Imaging studies if imaging is used for response assessment.
- 3.3.4 Every 1 week between on-site assessments
- Telephone communication with patient to assess for any symptoms suggestive of an adverse event; this will be performed by physician or research nurse. Symptoms of myocarditis (chest pain, shortness of breath, swelling of ankles or feet) will be assessed.
  - Laboratory studies as follows: CBC w/differential, LFTs (ALT, AST, total bilirubin, alkaline phosphatase), BUN or serum urea level, creatinine, Ca, Mg, Na, K, Cl, LDH, glucose, amylase and lipase.

### 3.3.5 At completion of treatment

- Targeted physical examination if clinically indicated which may include clinic-based flexible nasopharyngolaryngoscopy and/or tracheoscopy
- Vital signs and oxygen saturation at rest and after exertion
- Symptoms of myocarditis (chest pain, shortness of breath, swelling of ankles or feet) will be assessed
- Pregnancy test in women of childbearing potential
- CBC w/differential, LFTs (ALT, AST, total bilirubin, alkaline phosphatase), BUN or serum urea level, creatinine, Ca, Mg, Na, K, Cl, LDH, glucose, amylase, lipase, TSH with reflexive Free T4, Free T3
- TBNK
- Adverse events assessment
- Research blood:
  - 6 CPT tubes (48 mL) will be collected for immunological testing and processed as described in section 4.1.1. Attention [name], [name] contact [contact].
  - 1 SST tube (8 mL) will be obtained for serum collection and processed as described in section 4.1.1 . Attention [name], [name] contact [contact].
- Clinic-based flexible nasopharyngolaryngoscopy and/or tracheoscopy. This will include standard bright light endoscopy and may include videostroboscopy, and assignment of a Derkay score if the Derkay score is being used for response assessment. This endoscopic examination will be used to assess treatment response.
- Imaging studies if imaging is used for response assessment.
- Voice Handicap Index-10 assessment questionnaire.
- Exam under anesthesia (sedation or general anesthesia) including rigid and/or flexible endoscopy with biopsies to perform standard of care papilloma debulking, to obtain biopsies for research and to validate complete response or the presence of persistent disease. These tests will be done 2 and 6 weeks after the first dose of avelumab for all patients. The same tests will be repeated 12 weeks after the first dose for patients that demonstrate a partial response and receive an additional 6 weeks of treatment.

### 3.3.6 Follow-up studies

- Patients who experience a complete response or partial response will be evaluated every 6 weeks x 3, then every 12 weeks x 3, then every 26 weeks x 2 or until disease progression (+/- 10 days for each time point). After completing the first 2 years' worth of follow up clinic visits, patients will be contacted annually (+/- one month)

for 3 years (a total of 5 years follow up) for patient status, dates of disease recurrence and interventions to treat recurrent disease.

- Patients who do not experience a response to treatment will be contacted annually (+/- one month) for 2 years following the last dose of study drug to document additional disease recurrence and treatments that they have received.
- Evaluations will include:
  - Interval directed history and physical
  - CBC w/differential, LFTs (ALT, AST, total bilirubin, alkaline phosphatase), BUN or serum urea level, creatinine, Ca, Mg, Na, K, Cl, LDH, glucose, amylase, lipase, TSH with reflexive Free T4, Free T3
  - TBNK
  - Vital signs and oxygen saturation at rest and after exertion
  - Clinic-based flexible nasopharyngolaryngoscopy and/or tracheoscopy including standard bright light endoscopy and videostroboscopy with assignment of a Derkay score
  - Voice Handicap Index-10 assessment questionnaire.
  - Research blood: At each clinic visit and at subsequent time points at the discretion of the patient and the investigators:
    - 6 CPT tubes (48 mL) will be collected for immunological testing and processed as described in section 4.1.1. Attention [name], [name] contact [contact].
    - 1 SST tube (8 mL) will be obtained for serum collection and processed as described in section 4.1.1 . Attention [name], [name] contact [contact].
  - Adverse events will be followed until return to baseline or stabilization of event.
  - Imaging studies if imaging is used for response assessment.
  - Patients will be contacted 42 days (+/- 10 days) after the last dose of avelumab to check on patient's status.

### **3.4 DOSE MODIFICATIONS/DELAY**

Dose modifications are not permitted.

3.4.1 Doses will be delayed for the following:

- Any Grade 2 or greater drug-related adverse event with the following exceptions:
  - Grade 2 skin rash or fatigue
  - Grade 2 infusion reaction in which the full dose of the drug is safely infused, per instructions in section 3.4.4
- Any adverse event, laboratory abnormality, or intercurrent illness which, in the judgment of the investigator, warrants delaying the dose of study medication.
- Algorithms for management of toxicities are provided in Section 12.3.

### 3.4.2 Resuming treatment

Subjects may resume treatment with avelumab under any of the following circumstances:

- Any grade 2 event that resolves to grade 1 or less within 14 days without systemic steroid treatment
- Grade 3/4 rash that improves to Grade 1/2 with treatment
- Grade 2/3/4 endocrinopathy that responds to treatment/replacement therapy

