#### **3.6.1 Criteria for removal from protocol therapy**

Patients will be taken off treatment for the following:

- Completion of protocol therapy
- Participant requests to be withdrawn from active therapy
- The patient receives any other treatment for RRP or requires the use of any corticosteroids (> 10 mg daily prednisone equivalents) or other immunosuppressive medications.
- General or specific changes in the patient's condition render the patient unacceptable for further treatment on this study in the judgment of the investigator.
- Any Grade 3/4 drug-related adverse events with the exceptions as detailed in section 3.4.
- Disease progression
- Participant becomes pregnant

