#### 14.3.1 Gastrointestinal irAEs

Gastrointestinal irAEs		
Severity of Diarrhea / Colitis (NCI-CTCAE v4.03)	Management	Follow-up
Grade 1 Diarrhea: < 4 stools/day over Baseline Colitis: asymptomatic	Continue avelumab therapy Symptomatic treatment (for example, loperamide)	Close monitoring for worsening symptoms Educate subject to report worsening immediately If worsens: Treat as Grade 2 or 3/4
Grade 2 Diarrhea: 4 to 6 stools per day over Baseline; IV fluids indicated < 24 hours; not interfering with ADL Colitis: abdominal pain; blood in stool	Delay avelumab therapy Symptomatic treatment	If improves to Grade 1: Resume avelumab therapy If persists > 5 to 7 days or recur: 0.5 to 1.0 mg/kg/day methylprednisolone or equivalent When symptoms improve to Grade 1, taper steroids over at least 1 month, consider prophylactic antibiotics for opportunistic infections, and resume avelumab therapy per protocol. If worsens or persists > 3 to 5 days with oral steroids: Treat as Grade 3 to 4
Grade 3 to 4 Diarrhea (Grade 3): ≥ 7 stools per day over Baseline; incontinence; IV fluids ≥ 24 hrs; interfering with ADL Colitis (Grade 3): severe abdominal pain, medical intervention indicated, peritoneal signs Grade 4: life-threatening, perforation	Discontinue avelumab therapy per protocol 1.0 to 2.0 mg/kg/day methylprednisolone IV or equivalent Add prophylactic antibiotics for opportunistic infections Consider lower endoscopy	If improves: Continue steroids until Grade 1, then taper over at least 1 month If persists > 3 to 5 days, or recurs after improvement: Add infliximab 5 mg/kg (if no contraindication), Note: Infliximab should not be used in cases of perforation or sepsis

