14.3.2 Dermatological AEs

Dermatological AEs		
Grade of Rash (NCI-CTCAE v4)	Management	Follow-up

Grade 1 to 2            Covering ≤ 30% body surface area
	
Symptomatic therapy (for example, antihistamines, topical steroids)            Continue avelumab therapy
	
If persists > 1 to 2 weeks or recurs:            Consider skin biopsy            Delay avelumab therapy            Consider 0.5 to 1.0 mg/kg/day methylprednisolone IV or oral equivalent. Once improving, taper steroids over at least 1 month, consider prophylactic antibiotics for opportunistic infections, and resume avelumab therapy            If worsens:            Treat as Grade 3 to 4

Grade 3 to 4            Covering > 30% body surface area; life threatening consequences
	
Delay or discontinue avelumab therapy            Consider skin biopsy            Dermatology consult            1.0 to 2.0 mg/kg/day methylprednisolone IV or IV equivalent
	
If improves to Grade 1:            Taper steroids over at least 1 month and add prophylactic antibiotics for opportunistic infections            Resume avelumab therapy

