14.3.3 Pulmonary AEs

Pulmonary AEs		
Grade of Pneumonitis (NCI-CTCAE v4)	Management	Follow-up
Grade 1 Radiographic changes only	Consider delay of avelumab therapy Monitor for symptoms every 2 to 3 days Consider Pulmonary and Infectious Disease consults	Re-image at least every 3 weeks If worsens: Treat as Grade 2 or Grade 3 to 4
Grade 2 Mild to moderate new symptoms	Delay avelumab therapy Pulmonary and Infectious Disease consults Monitor symptoms daily, consider hospitalization 1.0 mg/kg/day methylprednisolone IV or oral equivalent Consider bronchoscopy, lung biopsy	Re-image every 1 to 3 days If improves: When symptoms return to near Baseline, taper steroids over at least 1 month and then resume avelumab therapy and consider prophylactic antibiotics If not improving after 2 weeks or worsening: Treat as Grade 3 to 4
Grade 3 to 4 Severe new symptoms; New / worsening hypoxia; life-threatening	Discontinue avelumab therapy Hospitalize Pulmonary and Infectious Disease consults 2 to 4 mg/kg/day methylprednisolone IV or IV equivalent Add prophylactic antibiotics for opportunistic infections Consider bronchoscopy, lung biopsy	If improves to Baseline: Taper steroids over at least 6 weeks If not improving after 48 hours or worsening: Add additional immunosuppression (for example, infliximab, cyclophosphamide, IV immunoglobulin, or mycophenolate mofetil)

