14.3.4 Hepatic AEs

Hepatic AEs		
Grade of Liver Test Elevation (NCI-CTCAE v4)	Management	Follow-up
Grade 1 Grade 1 AST or ALT > ULN to 3.0 x ULN and / or total bilirubin > ULN to 1.5 x ULN	Continue avelumab therapy	Continue liver function monitoring If worsens: Treat as Grade 2 or 3 to 4
Grade 2 AST or ALT > 3.0 to ≤ 5 x ULN and / or total bilirubin > 1.5 to ≤ 3 x ULN	Delay avelumab therapy Increase frequency of monitoring to every 3 days	If returns to Baseline: Resume routine monitoring, resume avelumab therapy If elevations persist > 5 to 7 days or worsen: 0.5 to 1 mg/kg/day methylprednisolone or oral equivalent and when LFT returns to Grade 1 or Baseline, taper steroids over at least 1 month, consider prophylactic antibiotics for opportunistic infections, and resume avelumab therapy
Grade 3 to 4 AST or ALT > 5 x ULN and / or total bilirubin > 3 x ULN	Discontinue avelumab therapy Increase frequency of monitoring to every 1 to 2 days 1.0 to 2.0 mg/kg/day methylprednisolone IV or IV equivalent Add prophylactic antibiotics for opportunistic infections Consult gastroenterologist Consider obtaining MRI/CT scan of liver and liver biopsy if clinically warranted	If returns to Grade 2: Taper steroids over at least 1 month If does not improve in > 3 to 5 days, worsens or rebounds: Add mycophenolate mofetil 1 gram (g) twice daily If no response within an additional 3 to 5 days, consider other immunosuppressants per local guidelines

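### Two Appendix C rows resume avelumab after systemic steroids for Grade 2 lung and liver events, although Section 3.6.1 takes those patients off treatment

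*Combined protocol and SAP*

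**What the plan says.** All references are to the combined protocol and SAP.

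- **Section 3.4.1** delays dosing for drug-related events of Grade 2 or higher. The exceptions are Grade 2 rash, fatigue and certain infusion reactions. It sends the reader to Section 12.3 for the toxicity algorithms, which actually stand in Section 14.3 (Appendix C).
- **Section 3.4.2** lists the circumstances in which a subject may resume. For Grade 2 events in general the entry is "Any grade 2 event that resolves to grade 1 or less within 14 days without systemic steroid treatment". The other two entries cover Grade 3/4 rash and Grade 2 to 4 endocrinopathy, each after a response to treatment.
- **Section 3.4.3** requires permanent discontinuation for drug-related Grade 3 or 4 events, apart from those that 3.4.2 allows.
- **Section 3.6.1** takes a patient off treatment who "requires the use of any corticosteroids (> 10 mg daily prednisone equivalents) or other immunosuppressive medications". This bullet has no exception. The bullet on Grade 3/4 events in the same list does carry the Section 3.4 exceptions.
- **Section 14.3.3, Grade 2 pneumonitis**, gives "1.0 mg/kg/day methylprednisolone IV or oral equivalent" as management, without a condition. When symptoms are near baseline, the follow-up column says "taper steroids over at least 1 month and then resume avelumab therapy and consider prophylactic antibiotics".
- **Section 14.3.4, Grade 2 hepatic**, has a steroid-free branch and a steroid branch. The steroid branch reads "If elevations persist > 5 to 7 days or worsen: 0.5 to 1 mg/kg/day methylprednisolone or oral equivalent". After recovery it says "taper steroids over at least 1 month, consider prophylactic antibiotics for opportunistic infections, and resume avelumab therapy".

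**The concern.** The same patient gets two opposite instructions about study drug. Someone with Grade 2 pneumonitis managed as Appendix C directs, or with a Grade 2 liver event that needed steroids, is off treatment under 3.6.1 and back on avelumab under Appendix C. No sentence in the protocol says which of the two prevails, and the pointer from 3.4.1 to the algorithms leads to the wrong section.

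What is at stake is re-exposure of a patient whose lung or liver toxicity has just needed systemic steroids, and uneven handling of similar patients. Pulmonary RRP is one of the routes into the trial, so some participants will already have lung disease.

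A smaller inconsistency sits beside this one. Read literally, the 3.6.1 steroid bullet also removes patients whose rash or endocrinopathy was treated with steroids above the limit, although 3.4.2 lets them restart.

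**Working it through.** **1. Do the Appendix C doses cross the 3.6.1 limit?**

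Inputs: a limit of 10 mg/day prednisone equivalents (3.6.1); 1.0 mg/kg/day methylprednisolone for pneumonitis (14.3.3); 0.5 to 1 mg/kg/day for hepatic events (14.3.4). The documents give no methylprednisolone-to-prednisone factor, so 1.0 to 1.25 is assumed.

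Weight at which the dose equals the limit = 10 / (dose per kg × factor).

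| Dose (mg/kg/day) | Factor 1.0 | Factor 1.25 |
|---|---|---|
| 0.5 | 10 / 0.5 = 20 kg | 10 / 0.625 = 16 kg |
| 1.0 | 10 / 1.0 = 10 kg | 10 / 1.25 = 8 kg |

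At an assumed 70 kg, 0.5 mg/kg/day is 35 to 43.75 mg/day and 1.0 mg/kg/day is 70 to 87.5 mg/day. Enrolment is restricted to adults, so anyone treated under either steroid instruction is over the limit.

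**2. Row against rule**

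| Event | Appendix C | 3.4.2 | 3.6.1 |
|---|---|---|---|
| Grade 2 pneumonitis | Steroids, taper, resume | Not listed: steroids were used | Off treatment |
| Grade 2 hepatic, persistent or worsening | Steroids, taper, resume | Not listed: steroids were used | Off treatment |
| Grade 2 hepatic, steroid-free branch | Resume at baseline | Listed if resolved within 14 days | Not triggered |

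The first two rows conflict with 3.6.1 however 3.4.2 is read. The third is not in dispute.

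**3. Doses at stake**

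Treatment is at most 6 doses on 14-day cycles, and only partial responders go beyond dose 3 (3.1.1, 3.2.1). After an event following dose k, max(0, 3 − k) Course 1 doses remain, and at most 6 − k doses in all.

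| Event after dose | 1 | 2 | 3 | 4 | 5 | 6 |
|---|---|---|---|---|---|---|
| Course 1 doses left | 2 | 1 | 0 | 0 | 0 | 0 |
| Most doses left, partial responder | 5 | 4 | 3 | 2 | 1 | 0 |

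**4. Timing of the first response assessment if Appendix C were followed**

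Section 3.3 postpones assessments when doses are delayed. Take the taper as 28 days, starting at improvement, with dosing resumed as it ends. Let d be the days from the last dose to improvement. The next dose was due 14 days after the last, so

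delay = d + 28 − 14 = d + 14 days.

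For an event after dose 1 or 2:

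- d close to 0: delay about 14 days, assessment at about week 6 + 2 = 8.
- d = 4: delay 18 days, assessment at 6 + 18/7 = about week 8.6.
- d = 14 (improvement on the day the next dose was due): delay 28 days, assessment at week 10.

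**5. Design figures**

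Section 9 gives a probability of early termination of 54.0% under the null. This reproduces: 0.95^12 = 0.540. With stages of 12 and 37 patients and success at 4 or more complete responses, the type I error is 0.093 and the power 0.902, within the planned 0.10 and 0.90. None of these depends on the restart rule.

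**The case against.** The best defence is that the protocol already gives a usable answer. Section 3.6.1 is mandatory and plain, restart has its own section, and Appendix C is introduced only as guidance on managing toxicity. Dosing takes place at one centre, and the team discusses each patient every two weeks (6.4.1). All of this makes divergent handling less likely. It does not remove the contradiction, because the two rows give direct instructions about study drug and nothing ranks them below Section 3. The 10 mg/day threshold also looks deliberate, since exclusion 2.1.2.3 uses it too.

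A reader might infer more than the documents support, in five ways:

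- **That 3.4.2 itself forbids these restarts.** Its wording is permissive and it leaves these cases out by omission; 3.4.3 makes discontinuation permanent only for Grade 3/4 events. The explicit bar is 3.6.1.
- **That all of Appendix C conflicts with Section 3.** The colitis row says "and resume avelumab therapy per protocol", which can be read as deferring to Section 3. The Grade 1 to 2 rash row says "Consider 0.5 to 1.0 mg/kg/day methylprednisolone IV or oral equivalent", so a conflict arises only if the option is taken up.
- **That Grade 2 infusion reactions conflict too.** In 3.4.4 corticosteroids appear as one example within the severity definition, not among the treatment modifications. The documents do not say that a single symptomatic dose triggers a limit expressed per day.
- **That the first assessment always slips to week 10 or beyond.** That ignores the 14-day interval already running. It holds only when improvement comes on or after the day the next dose was due.
- **That 3.4.2 should also admit steroid-treated Grade 1/2 rash, for proportionality.** That would be a new clinical permission, and the documents do not settle it.

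It is also fair to say that a precedence sentence does not harmonise the places where Appendix C is stricter than 3.4.2, such as recovery to baseline in the steroid-free hepatic branch. Those differences err towards caution and are not part of this point.

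**Conclusion.** The conflict is real and confined to two places: Grade 2 pneumonitis, and the steroid branch of Grade 2 hepatic events. In both, Appendix C resumes avelumab in a patient whom 3.6.1 has taken off treatment and whom 3.4.2 does not list for restart. The missing rash and endocrinopathy exception in the 3.6.1 steroid bullet and the outdated cross-reference in 3.4.1 are secondary.

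The size is bounded. The most at stake is the case of an event after dose 1, as tabulated above. If the row were followed, the first assessment would come at about week 8 at the earliest. That timing rests on a 28-day month and on resumption at the end of the taper; the hepatic row does not spell out that order as clearly as the pneumonitis row does. The dose comparison rests on the assumed conversion factor, but the margin is wide for any adult.

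How often this would arise is unknown, because the documents give no frequency for these events in RRP. Removal from treatment is not removal from study, so response can still be assessed. The sample size, stage rule, error rate and power stand. This is a safety-rule contradiction that should be corrected, not a threat to the primary analysis.

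**What to change.** Amend the wording as follows.

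- **Section 3.4:** state that 3.4.2, 3.4.3 and 3.6.1 govern restart and that Appendix C may not relax them. Say expressly that Appendix C's permanent discontinuation for immune-mediated myocarditis stays in force. Change the 3.4.1 cross-reference from 12.3 to 14.3.
- **Section 14.3.3 (Grade 2) and the steroid branch of 14.3.4 (Grade 2):** replace resumption with an instruction not to resume, citing 3.4.2 and 3.6.1. Leave the steroid-free hepatic branch as it is.
- **Section 3.6.1, steroid bullet:** add an exception for steroid courses given for rash or endocrinopathy that meet 3.4.2.

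The cost is that a few patients with steroid-treated Grade 2 lung or liver events receive fewer doses. Visits, stage rules and sample size do not change. Which rule is clinically better is for the sponsor to decide. If it prefers to allow restart after steroids, it should instead amend 3.4.2 and 3.6.1 to say so. Either way, one rule should remain.
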